8.2. Study monitoring

As per ICH-GCP 5.18 and FDA 21 CFR 312.50, clinical protocols are required to be adequately monitored by the study sponsor. Research monitors will be managed by:

Emissary International LLC
CEO: [name], PD, CCRA, PMP
[name]
[name]

Research monitors will verify that

- (1) There is documentation of the informed consent process and signed informed consent documents for each subject
- (2) There is compliance with recording requirements for data points
- (3) All SAEs are reported as required
- (4) Individual subjects' study records and source documents align
- (5) Investigators are in compliance with the protocol.
- (6) Regulatory requirements as per Office for Human Research Protections-OHRP), FDA, and applicable guidelines (ICH-GCP) are being followed.

8.3. Halting Criteria for the Study

The study enrollment and dosing will be stopped and an ad hoc review will be performed if any of the specific following events occur or, if in the judgment of the study physician, subject safety is at risk of being compromised:

- I. Unexpected death of a dosed subject in relation to infusion
- II. Occurrence of a life-threatening allergic/hypersensitivity reaction (anaphylaxis), manifested by bronchospasm with or without urticaria or angioedema requiring hemodynamic support with pressor medications or mechanical ventilation.
- III. One subject with an unexpected SAE associated with study product.
- IV. Two subjects with a Grade 3 or higher toxicity for the same parameter associated with study product.
- V. An overall pattern of symptomatic, clinical, or laboratory events that the medical monitor, ISM, or SMC consider associated with study product and that may appear minor in terms of individual events but that collectively may represent a serious potential concern for safety.
- VI. Any other event(s) which is considered to be a serious adverse event in the good clinical judgment of the responsible physician. This will be appropriately documented.

Interim Analyses for efficacy: There will be two formal review of interim results. The first will occur after 15 infections which is expected to occur near 150 participants reaching day 28 and the second after 50% of the total recruitment (n=500) has been achieved and these individuals followed to at least day 28. Interim analyses will only be adjusted for age. Stopping guidelines will be based on O’Brien-Flemming boundary. The interim analysis Z-value boundary of 3.03 (nominal p-value of 0.0011, spent alpha 0.0011), 2.38 (0.0087, 0.008), and 1.68 (0.464, 0.408) for a one-sided test with Type 1 of 0.05.

Special considerations for death:

Furthermore, given that ADE may be an issue with convalescent antibody treatment, out of an abundance of caution we will monitor the number of subjects in each trial arm that progresses to death. Given that we plan to recruit 75 participants in each arm and with the following assumptions 1) 20% of those in standard arm progress to symptomatic infection, 2) 5% in the anti-SARS-CoV-2 treatment arm are expected to progress to symptomatic infection, and 3) 1.4% of those with symptomatic infection progress to death, the probability of observing one death in either arm is unlikely (Table 1). Even with a higher symptomatic case fatality rate of 2.7% that has been estimated for those >64 years in Wuhan, China (Table 1) [Wu JT, LeungK, Bushman M, et al. Estimating Clinical Severity of COVID-19 from the transmission dynamics in Wuhan, China. *Nature Med*]. However, it is possible that more than one death may be seen by random chance in the sample that we accrue. Therefore, we will monitor the number of subjects that die and thoroughly evaluate whether each death is likely due to anti-SARS-CoV-2 plasma (definite, probable, possible, or unlikely). The DSMB will be unmasked for all interim analyses and reviews for safety. It is likely if 2 deaths occur in intervention arm that the DSMB would need to consider stopping due to safety concerns as two deaths would be highly unlikely (Table 2). After at least 50% of trial participants have accumulated follow-up, the number of subjects that progress to this stage will be presented to the masked DSMB and formally asked whether they see a clinically meaningful difference between trial arms that trigger an unmasking of the DSMB. This interim safety analysis will adjust for factors related to mortality including age and presence of cardiopulmonary comorbidities.

Table 1: Binomial probability of at least one death among each treatment arm by overall symptomatic case fatality rate and for those >64 years of age as estimated in Wuhan, China

Symptomatic Case Fatality Rate	Standard Plasma arm Expected Symptomatic N=15 participants	Anti-SARS-CoV-2 Plasma arm Expected Symptomatic N=4 participants
1.4%	0.191	0.055
2.7%	0.337	0.10

Table 2: For 1, 2, or 3 deaths observed among the expected number of symptomatic cases, the event probability of death (95% CI) and the probability that this would be observed under the overall symptomatic case fatality rate of 1.4% from Wuhan, China

	Standard Plasma Arm			Anti-SARS-CoV-2 Plasma arm		
	# of deaths	Point Estimate of Mortality	95% Confidence Interval	Probability of occurring under true symptomatic case fatality rate of 0.014	Point Estimate of Mortality	95% Confidence Interval
1	0.07	(0.002, 0.319)	0.19	0.25	(0.006, 0.806)	0.05
2	0.13	(0.017, 0.405)	0.018	0.50	(0.068, 0.932)	0.001
3	0.20	(0.043, 0.481)	0.001	0.75	(0.194, 0.993)	<0.0001

Special considerations for ARDS: Given that ARDS is a significant potential consequence of COVID-19 and potentially a sign of ADE, we will monitor participants for development of ARDS as a medical consequence of concern by monitoring differences between participants receiving control plasma and anti-SARS-CoV-2 plasma. Given that we plan to recruit 75 participants in each arm and with the following assumptions 1) 20% of those in standard arm progress to symptomatic infection, 2) 5% in the anti-SARS-CoV-2 treatment arm are expected to progress to symptomatic infection, and 3) in an abundance of caution *as a worst case scenario* we will assume that 40% will progress to ARDS (in Wuhan the reported frequency of ARDS was 3.4% for all subjects and 40% among the group reaching the composite endpoint of ICU admission, ventilation or death). Under this scenario of assumed maximum severity, we are likely to see at least one case in both treatment arms (Table 1). Specifically, we would expect *six* participants in the control and *two* participants in the treatment arm to develop ARDS (table 4). After at least 50% of trial participants have accumulated follow-up, the number of subjects that progress to this stage will be presented to the masked DSMB and formally asked whether they see a clinically meaningful difference between trial arms. This interim analysis will adjust for factors related to worsening of COVID-19 such as age, prior lung disease, and presence of cardiopulmonary comorbidities.

Table 3: Binomial Probability of at least one ARDS case among each treatment arm for a worse case scenario of 40 and 50% of those developing symptoms progressing to ARDS

Proportion Developing ARDS	Standard Plasma arm Expected Symptomatic N=15 participants	Anti-SARS-CoV-2 Plasma arm Expected Symptomatic N=4 participants
40%	>0.999	0.870
50%	>0.999	0.938

Table 4: For a given number of observed ARDS cases among the control plasma and anti-SARS-CoV-2 plasma treatment arms, the point estimate, 95% confidence interval, and probability of ARDS occurring under an assumed true rate of 0.4 among those who become symptomatic

	Standard Plasma Arm	Anti-SARS-CoV-2 Plasma arm
--	----------------------------	-----------------------------------

# of ARDS	Point Estimate of ARDS	95% Confidence Interval	Probability of occurring under true ARDS rate of 0.40	Point Estimate of ARDS	95% Confidence Interval	Probability of occurring under true ARDS of 0.40
1	0.07	(0.002, 0.319)	0.007	0.25	(0.006, 0.806)	>0.99
2	0.13	(0.017, 0.405)	0.036	0.50	(0.068, 0.932)	>0.99
3	0.20	(0.043, 0.481)	0.186	0.75	(0.194, 0.994)	0.309
4	0.27	(0.078, 0.551)	0.430	1.00	(0.398, 1.00)	0.026
6	0.40	(0.163, 0.677)	>0.99			
9	0.60	(0.323, 0.837)	0.122			
10	0.67	(0.384, 0.882)	0.061			

Upon completion of this review and receipt of the advice of the ISM or SMC, it will be determined if study entry or study dosing should be interrupted or if study entry and study dosing may continue according to the protocol.

Halting Criteria/Rules for Subject Infusion

Infusion of study drug will be halted if any of the following manifestations of anaphylaxis develop and will not be restarted:

- Skin or mucous membrane manifestations: hives, pruritus, flushing, swollen lips, tongue or uvula
- Respiratory compromise: dyspnea, wheezing, stridor, hypoxemia
- A decrease in systolic blood pressure to < 90 mmHg or >30% decrease from baseline or a diastolic drop of >30% from baseline.
- Tachycardia with an increase in resting heart rate to > 130bpm; or bradycardia <40 that is associated with dizziness, nausea or feeling faint.
- Syncope
- Confusion
- Any other symptom or sign which in the good clinical judgment of the study clinician or supervising physician warrants halting the infusion. For example, the rapid onset of gastrointestinal symptoms, such as nausea, vomiting, diarrhea, and cramps, for instance, may be manifestations of anaphylaxis and may warrant an immediate halt prior to meeting full SAE criteria

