5. STATISTICAL CONSIDERATIONS

5.1. Sample Size and Power Considerations

The planned sample size for the trial is 500 subjects, randomized in a 1:1 ratio to convalescent titer anti-SARS CoV-2 plasma vs SARS-CoV-2 non-immune plasma.

To evaluate the power of the study, the following assumptions were made:

- a. The primary analysis will compare efficacy/prevention in the convalescent titer and SARS-CoV-2 non-immune plasmas groups using proportional odds model and a one-sided Type I error rate (alpha) of 0.05 (i.e., for superiority) and Type II error rate (beta) of 0.2
- b. It is anticipated that very few of these subjects will be randomized and not start study plasma infusion (and so be excluded from the primary analysis) or be lost to follow-up prior to Day 28 (and so have missing data for the primary endpoint).

- c. 13% incidence of symptomatic disease in exposed individuals treated with SARS-CoV-2 non-immune plasma
- d. 6.5% incidence of symptomatic disease in exposed individuals treated with anti-SARS CoV-2 plasma

We estimate a sample size of 488 patients (244 in each arm) would be sufficient to detect a difference in outcomes between those two arms with a power of 0.8. To allow for some loss-to-followup, we have rounded our target sample to 500 patients.

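### The DSMB's death and ARDS reference tables (Protocol 8.3, Tables 1-4) are computed for 75 per arm and 20% vs 5%, not for the planned 250 per arm and 13% vs 6.5%

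*Protocol*

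**What the plan says.** Protocol 8.3, in the special considerations for death, sets out its basis: "Given that we plan to recruit 75 participants in each arm and with the following assumptions 1) 20% of those in standard arm progress" (that is, develop symptoms), then 5% in the HCIP arm and a symptomatic case fatality of 1.4%, with 2.7% as the rate for people over 64. The ARDS paragraph repeats the 75 per arm and the 20% and 5%. It takes 40% progression to ARDS as a declared worst case and quotes 3.4% as the rate among all subjects in Wuhan. Tables 1 to 4 all follow from 15 control and 4 HCIP symptomatic participants.

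Two statements rest on the death tables. One is that "the probability of observing one death in either arm is unlikely (Table 1"). The other is that, with two deaths in the intervention arm, the DSMB "would need to consider stopping due to safety concerns as two deaths would be highly unlikely (Table 2"). The ARDS text expects six control and two HCIP cases. Both formal reviews are timed "After at least 50% of trial participants have accumulated follow-up".

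The sample size section (Protocol 5.1) has a different design: "The planned sample size for the trial is 500 subjects, randomized in a 1:1 ratio", with "13% incidence of symptomatic disease in exposed individuals treated with SARS-CoV-2 non-immune plasma" and "6.5% incidence of symptomatic disease in exposed individuals treated with anti-SARS CoV-2 plasma". The SAP (Power and Sample Size) uses the same 500, 0.13 and 0.065. Protocol 8.3 itself uses the larger size for the interim efficacy looks: "the second after 50% of the total recruitment (n=500) has been achieved".

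**The concern.** The recruitment target and event rates behind the tables contradict the design in the same protocol. The HCIP column is affected most. It has half the symptomatic cases expected at the 50% review and a quarter of those expected at full enrolment, because both the sample size and the assumed effect differ (a 75% reduction instead of 50%).

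These are the only figures in the plan that tell the DSMB how surprising a given number of deaths or ARDS cases would be. Antibody-dependent enhancement is the theoretical risk behind them. The SAP's stopping guidelines ask for special attention to HCIP deaths and ARDS because they are improbable under the hypothesised effect, yet the likelihood is quantified only here, under a different effect. At stake is the calibration of a safety reference. Efficacy type I error and power are not affected.

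**Working it through.** **Inputs.** Protocol 8.3: 75 per arm, 20% and 5% symptomatic, fatality 1.4% or 2.7%, ARDS 40% worst case. Protocol 5.1: 250 per arm, 13% and 6.5%. The 50% review corresponds to 125 per arm.

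**Method, as in the tables.** Fix the symptomatic count N at its expected value and use the binomial:

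- P(at least 1) = 1 − (1 − p)^N
- P(at least 2) = 1 − (1 − p)^N − N·p·(1 − p)^(N−1)
- The Table 4 probabilities are two-sided exact binomial p-values against 0.40.

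**Reproducing the printed values.** 75 × 0.20 = 15 and 75 × 0.05 = 3.75, shown as 4.

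- Table 1: at 1.4%, 0.191 and 0.055; at 2.7%, 0.337 and 0.104.
- Table 2, two deaths: 0.018 and 0.0012.
- Table 3 at 40%: 0.9995 and 0.870.
- Table 4, HCIP: 0.309 for three cases and 0.026 for four.

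All agree with print, so the method is as described.

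**Expected cases under the planned design.**

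- 50% review: 125 × 0.13 = 16.25 and 125 × 0.065 = 8.1
- Full enrolment: 250 × 0.13 = 32.5 and 250 × 0.065 = 16.25

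**Worked example, two or more HCIP deaths at 1.4%.**

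- N = 4: 1 − 0.986^4 − 4(0.014)(0.986^3) = 0.0012
- N = 8: 1 − 0.986^8 − 8(0.014)(0.986^7) = 0.0052
- N = 16: 1 − 0.986^16 − 16(0.014)(0.986^15) = 0.0206

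| Quantity | Printed (N = 15 / 4) | 50% review (16 / 8) | Full enrolment (32 / 16) |
|---|---|---|---|
| At least 1 control death, 1.4% | 0.191 | 0.202 | 0.363 |
| At least 1 control death, 2.7% | 0.337 | 0.355 | 0.584 |
| At least 1 HCIP death, 1.4% | 0.055 | 0.107 | 0.202 |
| At least 1 HCIP death, 2.7% | 0.10 | 0.197 | 0.355 |
| At least 2 control deaths, 1.4% | 0.018 | 0.021 | 0.074 |
| At least 2 HCIP deaths, 1.4% | 0.001 | 0.005 | 0.021 |
| At least 2 HCIP deaths, 2.7% | not printed | 0.018 | 0.068 |
| At least 1 HCIP ARDS case, 40% | 0.870 | 0.983 | >0.999 |
| Four HCIP ARDS cases, two-sided p against 40% | 0.026 | 0.72 | 0.31 |
| One HCIP ARDS case, two-sided p against 40% | >0.99 | 0.16 | 0.004 |

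**Any death in the trial at 1.4%**, 1 − 0.986^N over both arms: 0.235 with the printed inputs (N = 19), 0.287 at the 50% review (N = 24), 0.492 at full enrolment (N = 48).

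**Expected ARDS cases, control and HCIP.** At 40%: 16.25 × 0.4 = 6.5 and 8.125 × 0.4 = 3.25 at the 50% review, then 13 and 6.5 at full enrolment, against the printed six and two. At 3.4%: 0.55 and 0.28, then 1.1 and 0.55.

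**Sensitivity to fixing N.** Letting the symptomatic count vary (125 or 250 per arm, event probability 0.065 × fatality) gives two or more HCIP deaths as 0.0060 and 0.022 at 1.4%, and 0.021 and 0.072 at 2.7%. The conclusion does not depend on that simplification.

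**Could 75 per arm mean the first interim look, near 150 participants?** No. The text presents it as the number to be recruited, and 13% and 6.5% of 75 give about 10 and 5 cases, not 15 and 4.

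**The case against.** The strongest reply is that the mismatch changes little where it counts. At the 50% review the control column is almost unchanged, and two HCIP deaths still have probability 0.005, or 0.018 at the older-age fatality rate. Near 150 participants the value is 0.002 (N = 5), close to print. The largest shifts occur at full enrolment, when every participant has had the single transfusion and little remains to halt. The DSMB must also weigh causality for each death and an adjusted comparison between arms, with no count as a binding trigger. For deaths, too small a denominator errs towards caution. As for one death being unlikely, the protocol already appears to apply that word to a printed 0.337, so 0.36 is not a clear break.

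Most of this stands as a limit on the consequences: no wrongful halt is shown, and two HCIP deaths remain uncommon at 1.4%. It does not rescue the tables. The wording on a single death does fail at full enrolment: a control death at 2.7% has probability 0.58, and any death in the trial at 1.4% has probability 0.49. For ARDS the distortion runs both ways. Against the 40% worst case, four HCIP cases look extreme in print but are ordinary under the planned design. One case looks typical in print but would be far fewer than expected at full enrolment. Table 4 also stops at four HCIP cases, while the same worst case now implies 6.5 at full enrolment.

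**Conclusion.** The concern holds. Tables 1 to 4 are correctly calculated for a design that this protocol does not have. The error is mainly in the HCIP column: two or more deaths is about 4.5 times as probable as the tables imply at the 50% review (0.0052 against 0.00115) and about 18 times at full enrolment (0.0206 against 0.00115). The control column is close at the 50% review (15 against 16 cases) and too small by about half at full enrolment.

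This should be corrected, though it does not threaten the trial's main conclusions. The figures assume the protocol's own 13% and 6.5%, its fatality and ARDS rates, equal allocation, and a review at exactly 125 per arm. A later review moves the values towards the full-enrolment column. At the 3.4% ARDS rate, four HCIP cases would remain a signal even at full enrolment (probability of four or more 0.002 at N = 16), so the correction does not make such a cluster reassuring.

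**What to change.** Recompute Tables 1 to 4 and the expected counts in Protocol 8.3 with 250 per arm and 13% and 6.5%. Show the 50% review (16 and 8 symptomatic) and full enrolment (about 32 and 16) side by side, and extend the HCIP rows of Table 4 past four cases. Replace the 75 per arm and the 20% and 5% in both paragraphs. Reword the statements on one death and on two HCIP deaths so that they quote the new values and the point in the trial to which they apply. Keep 40% ARDS labelled as the worst case; a row at 3.4% would be a useful addition but is optional. Send the revised tables to the DSMB. No new stopping trigger is needed.

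The cost is four recalculated tables, corrected inputs and counts, and two reworded statements, with no change to conduct or data collection.

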### **Stopping guidelines:**

The trial can be terminated for any of the following reasons:

1. One treatment arm is superior to the other with substantial confidence that exceeds the planned boundaries;
2. Neither treatment arm is significantly different from the other and the possibility of achieving a difference is less than 10% with full enrollment;
3. Side effects outweigh the potential benefits of treatment in one or both treatment arms;
4. Data quality is compromised;
5. Data accrual is too slow to finish the study in a reasonable time period after considering the pandemic course and the potential for secondary outbreaks of disease;

6. External data suggests an accepted answer to the study question and investigators are no longer conducting the study under equipoise;
7. The study question is no longer relevant to the clinical community;
8. Adherence to the treatment arms is poor, leading to poor data quality;
9. There is a loss of study resources to perform the study;
10. There is evidence of fraud or misconduct in the study.

Special attention will be given to progression to ARDS and to deaths in the HCIP treatment group given the low likelihood of these outcomes under the hypothesized treatment effect.

These stopping guidelines have been adapted from *Clinical Trials: A Methodological Perspective, 2nd Edition* (Piantadosi 2005).

References:

Benkeser, David, Iván Díaz, Alex Luedtke, Jodi Segal, Daniel Scharfstein, and Michael Rosenblum. 2020. "Improving Precision and Power in Randomized Trials for COVID-19 Treatments Using Covariate Adjustment, for Binary, Ordinal, and Time-to-event Outcomes." *Biometrics*, September. <https://doi.org/10.1111/biom.13377>.

Díaz, Iván, Elizabeth Colantuoni, Daniel F. Hanley, and Michael Rosenblum. 2019. "Improved Precision in the Analysis of Randomized Trials with Survival Outcomes, without Assuming Proportional Hazards." *Lifetime Data Analysis* 25 (3): 439–68. <https://doi.org/10.1007/s10985-018-9428-5>.

Díaz, Iván, Elizabeth Colantuoni, and Michael Rosenblum. 2016. "Enhanced Precision in the Analysis of Randomized Trials with Ordinal Outcomes." *Biometrics* 72 (2): 422–31. <https://doi.org/10.1111/biom.12450>.

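### The probability cited for two deaths in the convalescent-plasma arm assumes that the plasma already prevents disease, so it is not the chance of two deaths under a harmless but ineffective plasma

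*Protocol*

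**What the plan says.** The special considerations for death in Protocol section 8.3 start from "Given that we plan to recruit 75 participants in each arm" and two symptomatic rates: "20% of those in standard arm progress to symptomatic infection", and "5% in the anti-SARS-CoV-2 treatment arm are expected to progress to symptomatic infection". This gives 15 expected symptomatic cases in the control arm and 4 in the convalescent-plasma (HCIP) arm. Table 2 then gives, for each death count, "the probability that this would be observed under the overall symptomatic case fatality rate of 1.4% from Wuhan, China". For two deaths it shows 0.018 in the standard-plasma column and 0.001 in the HCIP column.

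The text draws its prompt from the HCIP column. It considers it likely that, after two deaths in the intervention arm, "the DSMB would need to consider stopping due to safety concerns as two deaths would be highly unlikely (Table 2").

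The section also mentions a "higher symptomatic case fatality rate of 2.7% that has been estimated for those >64 years in Wuhan, China". That rate enters Table 1, which concerns at least one death. It does not enter Table 2, which supports the prompt.

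The SAP, under Stopping guidelines, gives no count. It promises special attention to ARDS and to deaths in the HCIP group "given the low likelihood of these outcomes under the hypothesized treatment effect".

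**The concern.** Section 8.3 watches deaths because of possible antibody-mediated enhancement. The reference for a harm signal should therefore be a plasma that does no harm. The HCIP column of Table 2 uses a narrower reference: a plasma that does no harm and also achieves a 75% reduction in symptomatic disease (5% against 20%). Whether plasma reduces disease at all is the question the trial is asking.

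If the plasma is inert, HCIP recipients fall ill at the control rate and deaths follow at the ordinary case fatality. Measured against the printed 0.001, those deaths look far more surprising than they are, and lack of efficacy can be mistaken for evidence of harm. What is at stake is how much weight a DSMB gives to two HCIP-arm deaths when it weighs stopping.

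The fatality rate adds to this. Eligibility (section 4.3.1) begins at 18 with no upper age limit, and section 6 foresees residents of nursing facilities, yet the two-death probability is shown only at the all-age rate.

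**Working it through.** **Inputs.** From Protocol section 8.3: 75 per arm; symptomatic rates 20% (control) and 5% (HCIP); fatality among symptomatic cases 1.4% overall and 2.7% over 64 years. From Protocol section 5.1: 500 participants 1:1, so 250 per arm; symptomatic rates 13% and 6.5%.

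**Formula.** For n cases with fatality f, P(at least 2 deaths) = 1 − (1−f)^n − n·f·(1−f)^(n−1).

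**Step 1: reproduce Table 2.**
- HCIP arm: 75 × 0.05 = 3.75, rounded to 4. With f = 0.014: 1 − 0.986^4 − 4 × 0.014 × 0.986^3 = 0.00115 (printed 0.001).
- Control arm: 75 × 0.20 = 15. With f = 0.014: 1 − 0.986^15 − 15 × 0.014 × 0.986^14 = 0.0182 (printed 0.018).

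The table's arithmetic is right. The question is which scenario the HCIP column describes.

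**Step 2: no benefit, section 8.3's own inputs.** The HCIP arm now has 15 cases.
- f = 0.014: 0.0182. Ratio 0.01823 / 0.00115 ≈ 16.
- f = 0.027: 0.0607, a ceiling that treats every case as over 64.
- For comparison, changing only the fatality rate (4 cases, f = 0.027) gives 0.0042, about 3.7 times 0.00115. Most of the gap therefore comes from the assumed benefit.

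**Step 3: current design.** Here deaths are Binomial(N, symptomatic rate × f). For example, 0.13 × 0.014 = 0.00182 per participant.

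| HCIP participants | Fatality | No benefit (13%) | Hypothesised benefit (6.5%) | Ratio |
|---|---|---|---|---|
| 250 (whole trial) | 1.4% | 0.077 | 0.022 | 3.5 |
| 250 (whole trial) | 2.7% (ceiling) | 0.219 | 0.072 | 3.0 |
| 125 (50% review) | 1.4% | 0.022 | 0.006 | 3.7 |
| 125 (50% review) | 2.7% (ceiling) | 0.072 | 0.021 | 3.5 |

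Fixing the number of cases at 32 to 33 instead (13% of 250 = 32.5) gives 0.074 to 0.078 at 1.4%, so the choice of binomial form hardly matters.

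**Step 4: split the gap.** From 0.00115 to 0.0767 is a factor of about 66. Moving to the current inputs with benefit still assumed takes 0.00115 to 0.0222, a factor of about 19. Removing the assumed benefit takes 0.0222 to 0.0767, a factor of about 3.5. The benefit assumption weighs more on section 8.3's inputs (16-fold) because they build in a 75% reduction, whereas section 5.1 assumes 50%.

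**The case against.** The case for leaving the text alone has five parts.

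- *The no-benefit figure is already printed.* On section 8.3's inputs it equals the control-arm 0.018, which is still small. This is true and limits the point. But that figure is labelled as the control arm and is not linked to the prompt, and no two-death probability at 2.7% appears anywhere.
- *Table 2 is conditional on the number of symptomatic cases.* A DSMB with unmasked data would see roughly the control number of cases if plasma were inert, and could discount the 0.001. A careful board might do so, but the sentence in section 8.3 gives it only the 4-case figure.
- *This is a prompt, not a boundary.* Section 8.3 says the DSMB would consider stopping, concedes that more than one death may occur by chance, and has each death assessed for its relation to plasma. It also plans a between-arm comparison at 50% follow-up, adjusted for age and cardiopulmonary comorbidity. (The section is inconsistent on whether the DSMB is masked, but the comparison is planned either way.) This stands. A reader might infer that two deaths alone would stop the trial or brand the product harmful; the documents do not support that.
- *2.7% is extreme.* It applies to the whole trial only if every case is over 64. The documents give no age mix, and section 3.3 expects many health care workers and first responders. It serves as an upper range only.
- *A sensitive prompt is a legitimate choice.* It is, and nothing here disputes the count. The point concerns the probability offered to justify it.

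**Conclusion.** The point holds, at moderate size. The 0.001 is the chance of two HCIP deaths if the plasma works as hoped, and it is used where the chance under a harmless, ineffective plasma belongs. On section 8.3's inputs the appropriate figure is 0.018 at 1.4%, about 16 times larger, with a ceiling of 0.061. On the current design it is 0.077 over the whole trial (ceiling 0.219), against 0.022 (0.072) with the hypothesised benefit.

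A reader might set 0.077 or 0.219 directly against 0.001 and attribute the whole difference to the assumed benefit. That is not supported: the 0.001 rests on 75 per arm and 20%/5%, the larger figures on 250 per arm and 13%. On like inputs the assumed benefit is worth about 3 to 3.5-fold over the whole trial. The remainder is the separate failure to update section 8.3 to section 5.1.

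The figures assume that deaths arise only from symptomatic COVID-19, independently, at the plan's quoted rates. Deaths from other causes would raise all of them.

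**What to change.** When Tables 1 and 2 of Protocol section 8.3 are reconciled with section 5.1:

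- compute the HCIP-arm two-death probability with the HCIP symptomatic rate set equal to the control rate, at 1.4%, with 2.7% shown as an upper range;
- keep the hypothesised-benefit figure as a second, labelled scenario;
- cite the no-benefit probability in the sentence that now rests on Table 2;
- name no benefit as the reference in the SAP's Stopping guidelines, in place of the hypothesised effect.

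The cost is a recalculated table and a few lines of wording in each document, with no new data or participants. The downside is that the stated probability becomes less extreme, so two deaths alone carry less weight as evidence of harm. The count at which the DSMB considers action is for the sponsor and the DSMB to decide.
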